6 SAFETY EVALUATIONS

6.1 Adverse Events

Adverse events mean any sign, symptom, syndrome or illness that occurs or worsens during the use of the study device/drug, regardless of causality. Symptoms of abnormal laboratory values and clinically significant asymptomatic laboratory values will constitute adverse events. A medical condition that is present when the subject enters the study is not defined as an adverse event, unless this medical condition worsens after the study drug has been administered.

The Investigator, the safety physician of The Rogosin Institute, and the Safety Data Monitoring Board will be responsible for monitoring the safety parameters that are collected in the study. As of their review of the safety/toxicity data from Phase I in June 2009, they found no adverse events attributable to the macrobeads. The Safety Data Monitoring Board will independently review all safety parameters and safety results in the study.

The description of the adverse events will use the CTCAE v3.0 definitions (issued on December 12, 2003) to define the severity or intensity of the adverse events and clinical laboratory abnormalities. The coding of the adverse events will use the most current version of the Medical Dictionary for Regulatory Agencies (MedDRA). The coding will include reported term, preferred term, and classification of the System, Organ, Class (SOC). The coding of concomitant medications will use the latest version of the WHO Drug Dictionary (WHODD).

6.2 Classification of Adverse Events by Intensity

If the intensity of the adverse event is not described in the CTCAE v3.0, the Investigator will rate the intensity of the adverse event according to the following scale.

- Grade 1** **Mild AE.** The adverse event is transient and easily tolerated by the subject.
- Grade 2:** **Moderate AE.** The adverse event causes the subject discomfort and interrupts the subject's normal activities.
- Grade 3:** **Severe AE.** The adverse event causes considerable interference with the subject's normal activities.
- Grade 4:** **Life-threatening or Disabling AE.**
- Grade 5:** **Death**

6.3 Classification of Adverse Events by Relationship to Study Drug

The Investigator will also assess the relationship of the adverse event to the RENCA macrobead according to the following definitions:

Not related:

The adverse event does not follow a reasonable temporal sequence from administration of the study drug, or that can be reasonably explained by other factors, including underlying disease, complications, concomitant drugs or concurrent treatment. Even if the investigator feels there is no relationship to the study drug, the adverse event must be reported.

Remote:

The adverse event follows an improbable temporal sequence to study drug administration and in which underlying disease, complications, concomitant drugs or concurrent treatment offers a plausible explanation.

Possibly related:

The adverse event follows a reasonable temporal sequence from administration of the study drug (including the course after withdrawal of the study drug), that can not exclude the possibility of the study drug involvement, although other factors such as underlying disease, complications, concomitant drugs or concurrent treatment are presumable.

Probably related:

The adverse event follows a reasonable temporal sequence from administration of the drug (including the course after withdrawal of the drug), and that can exclude the possibilities of other factors, such as underlying disease, complications, concomitant drugs or concurrent treatment, other than the study drug.

These events will be reported to the IRB and FDA according to their requirements.

6.4 Serious Adverse Events

A serious adverse event is any untoward medical occurrence, regardless of relationship to the study drug and intensity, at any dose that:

- Results in death
- Is life-threatening – (which is defined as an event in which the patient or subject was at risk of death at the time of the event; it does not refer to an event which hypothetically might have caused death if it were more severe)
- Requires in-patient hospitalization or prolongation of existing hospitalization
- Results in a persistent or significant disability/incapacity
- Is a congenital anomaly/birth defect
- Is an important medical event – (which is defined as a medical event(s) that may not be immediately life-threatening or results in death or hospitalization but, based upon appropriate medical and scientific judgment, may jeopardize the subject or may require intervention (e.g., medical, surgical) to prevent any of the other serious outcome listed in the definition above. Examples of such event include, but are not limited to, intensive treatment in an emergency room or at home or allergic bronchospasm; blood dyscrasias, or convulsions that do not result in hospitalization

Adverse events classified as “serious” require expeditious handling and reporting to the product’s sponsor to comply with regulatory requirements. Any SAE must be reported as quickly as possible after learning of the event by telephone or by a facsimile transmission of a Serious Adverse Event Form. The reporting requirements are outlined in The Rogosin Institute Clinical Research Program Operating Procedure.

Serious adverse events (i.e., any adverse event that meets the FDA definition and has a CTCAE Grade of 3-5) in subjects receiving the RENCA macrobeads will be reported as soon as possible to:

[name]
Attending Physician
The Rogosin Institute
[name]
[name]

Office: [contact]
Service: [contact]
[contact]

If only limited information is initially available, follow-up reports will be required, and must be submitted to the study contact named above no greater than fifteen (15) days of receipt of additional information. Copies of SAE reports are to be forwarded to the DSMB as per Weill Cornell Medical College DSMB/IRB procedures and to the IND as per FDA current reporting procedures.

All adverse events will also be evaluated for intensity using the CTCAE v3.0.

Any serious adverse events 120 days after the last implantation, not related to the RENCA macrobeads will not need to be reported to the sponsor.

6.5 Stopping Rule for an Individual Subject

If the sponsor, investigator, study monitor, Data Safety Monitoring Board (DSMB) or officials from the Food and Drug Administration (FDA) discover conditions arising during the study that indicate that the study should be halted or that the study center should be terminated, this action may be taken after appropriate consultation between the sponsor and investigator. Conditions that may warrant termination of the study include, but are not limited to, the following:

- The discovery of an unexpected, serious, or unacceptable risk to the patients enrolled in the study
- A decision on the part of the sponsor to suspend or discontinue testing, evaluation, or development of the product

6.5.1 Maximum Tolerated Dose/Dose Limiting Toxicity

In this protocol, there will be four implantations of macrobeads. The single dose (i.e., 8 macrobeads per kilogram) was previously shown to be well tolerated. In this study, the dose limiting toxicity (DLT) is most likely to be related to the number of implantations rather than the number of macrobeads implanted at each implantation.

Dose limiting toxicity (DLT) will be defined as

1. Any Grade 2 allergic reaction of generalized urticaria or any other grade ≥ 3 allergic reaction;
2. Any Grade ≥ 3 infection;
3. Any grade ≥ 3 local (intraperitoneal) reaction including peritoneal irritation or interference with intraperitoneal organ function; and
4. Any grade ≥ 3 hematologic or non-hematologic reaction.

This definition of DLT is in accord with the NCI Common Terminology Criteria for Adverse Events v3.0 (CTCAE).

6.6 Premature Termination of the Study

This protocol provides for four doses of the RENCA macrobeads. The dosage to be used at each implantation will be 8 RENCA macrobeads per kg of subject body weight. The Safety Committee, as well as the investigators, will review each instance of Grade 5 adverse event. In order to protect subjects from excessive toxicities possibly associated with the study treatment, the following stopping rule will be utilized: if 3 or more subjects experience a grade 5 adverse event deemed possibly related to treatment, accrual will be halted and a thorough investigation will take place before the re-opening of accrual may be considered.

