All available information from the imaging studies, tumor marker and other laboratory findings, as well as physical examination findings and quality of life measurements from Visit 5 will be reviewed to determine if a subject is cleared for the proposed anesthesia and second implantation of macrobeads. Assuming the subject is cleared, the second implantation will proceed as soon as possible.

5.1.10 Visit 6, Implant 2 / Study Day 0:

Beginning 3 months after the first implant, the subject will be scheduled for a second implant of the cancer macrobeads at a dosage of 8 macrobeads per kilogram body weight. Assuming that the subject's post-surgical condition is stable (as defined by standard post-operative criteria) and that the subject is taking oral fluids and soft foods at a minimum, the subject will be discharged to home care as soon as medically indicated which may be the same day as implantation.

If deemed medically and surgically safe by the operating surgeon, one or more biopsies of tumor mass will be taken during this procedure. Fresh frozen tissue and fixative-treated tissue will be sent to the laboratory for immunohistochemical and gene array analysis to determine any changes in tumor state that may have been the result of exposure to the cancer macrobeads.

5.1.11 Visit 7, Implant 2 / Study Day 14 ± 3 days:

A brief examination including the parameters listed below will be performed. Assuming that the wound examination is satisfactory, all sutures/staples will be removed by the surgeon who performed the laparoscopy or appropriate surrogate. In addition, the Investigator will also examine the subject.

The following data will be obtained:

- Vital signs with weight
- Physical examination with brief neurological exam
- CBC with differential WBC, platelet count
- Coagulation profile (PT, PTT and INR)
- Erythrocyte sedimentation rate
- Comprehensive Metabolic Panel with LD, GGT, CRP, direct bilirubin

- Cytokine panel
- CEA, CA 19-9, CA 125
- Circulating Tumor Cell Levels
- Monitoring of adverse events and concomitant medications
- Global clinical assessment
- Quality of life scale
- ECOG and Karnofsky Performance status rating
- Pain scale, if appropriate

5.1.12 Visit 8, Implant 2 / Study Day 30 ± 5 days:

The following data will be obtained:

- Vital signs with weight
- Physical examination with brief neurological exam
- CBC with differential WBC, platelet count
- Coagulation profile (PT, PTT and INR)
- Erythrocyte sedimentation rate

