All available information from the imaging studies, tumor marker and other laboratory findings, as well as physical examination findings and quality of life measurements from Visit 10 will be reviewed to determine if a subject is cleared for the proposed anesthesia and third implantation of macrobeads. Assuming the subject is cleared, the third implantation will proceed as soon as possible.

5.1.15 Visit 11, Implant 3 / Study Day 0:

Beginning 3 months after the second implant, the subject will be scheduled for a third implant of the cancer macrobeads at a dosage of 8 macrobeads per kilogram body weight. Assuming that the subject's post-surgical condition is stable (as defined by standard post-operative criteria) and that the subject is taking oral fluids and soft foods at a minimum, the subject will be discharged to home care as soon as medically indicated which may be same day as implantation.

If deemed medically and surgically safe by the operating surgeon, one or more biopsies of tumor mass will be taken during this procedure. Fresh frozen tissue and fixative-treated tissue will be sent to the laboratory for immunohistochemical and gene array analysis to determine any changes in tumor state that may have been the result of exposure to the cancer macrobeads.

5.1.16 Visit 12, Implant 3 / Study Day 14 ± 3 days:

A brief examination including the parameters listed below will be performed. Assuming that the wound examination is satisfactory, all sutures/staples will be removed by the surgeon who performed the laparoscopy or appropriate surrogate. In addition, the Investigator will also examine the subject.

The following data will be obtained:

- Vital signs with weight
- Physical examination with brief neurological exam
- CBC with differential WBC, platelet count
- Coagulation profile (PT, PTT and INR)
- Erythrocyte sedimentation rate
- Comprehensive Metabolic Panel with LD, GGT, CRP, direct bilirubin
- Cytokine panel
- CEA, CA 19-9, CA 125

- Circulating Tumor Cell Levels
- Monitoring of adverse events and concomitant medications
- Global clinical assessment
- Quality of life scale
- ECOG and Karnofsky Performance status rating
- Pain scale, if appropriate

5.1.17 Visit 13, Implant 3 / Study Day 30 ± 5 days:

The following data will be obtained:

- Vital signs with weight
- Physical examination with brief neurological exam
- CBC with differential WBC, platelet count
- Coagulation profile (PT, PTT and INR)
- Erythrocyte sedimentation rate

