for the proposed anesthesia and fourth implantation of macrobeads. Assuming the subject is cleared, the fourth implantation will proceed as soon as possible.

5.1.20 Visit 16, Implant 4 / Study Day 0:

Beginning 3 months after the third implant, the subject will be scheduled for a fourth implant of the cancer macrobeads at a dosage of 8 macrobeads per kilogram body weight. Assuming that the subject's post-surgical condition is stable (as defined by standard post-operative criteria) and that the subject is taking oral fluids and soft foods at a minimum, the subject will be discharged to home care as soon as medically indicated which may be same day as implantation.

If deemed medically and surgically safe by the operating surgeon, one or more biopsies of tumor mass will be taken during this procedure. Fresh frozen tissue and fixative-treated tissue will be sent to the laboratory for immunohistochemical and gene array analysis to determine any changes in tumor state that may have been the result of exposure to the cancer macrobeads.

5.1.21 Visit 17, Implant 4 / Study Day 14 ± 3 days:

A brief examination including the parameters listed below will be performed. Assuming that the wound examination is satisfactory, all sutures/staples will be removed by the surgeon who performed the laparoscopy or appropriate surrogate. In addition, the Investigator will also examine the subject.

The following data will be obtained:

- Vital signs with weight
- Physical examination with brief neurological exam
- CBC with differential WBC, platelet count
- Coagulation profile (PT, PTT and INR)
- Erythrocyte sedimentation rate
- Comprehensive Metabolic Panel with LD, GGT, CRP, direct bilirubin
- Cytokine panel
- CEA, CA 19-9, CA 125
- Circulating Tumor Cell Levels
- Ecotropic murine leukemia virus tests
- Monitoring of adverse events and concomitant medications
- Global clinical assessment

- Quality of life scale
- ECOG and Karnofsky Performance status rating
- Pain scale, if appropriate

5.1.22 Visit 18, Implant 4 / Study Day 30 ± 5 days:

The following data will be obtained:

- Vital signs with weight
- Physical examination with brief neurological exam
- CBC with differential WBC, platelet count
- Coagulation profile (PT, PTT and INR)
- Erythrocyte sedimentation rate
- Comprehensive Metabolic Panel with LD, GGT, CRP, direct bilirubin
- Cytokine panel
- CEA, CA 19-9, CA 125
- Circulating Tumor Cell Levels
- Ecotropic murine leukemia virus tests

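### The stopping rule for three possibly related deaths halts accrual but does not automatically hold implants 2–4 in subjects already enrolled

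*Protocol*

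**What the plan says.** The rule appears twice in the protocol, in section 6.6 and in Appendix 3 item 8. In both, the trigger is 3 or more subjects with a grade 5 adverse event judged possibly related to treatment. In both, the response is that "accrual will be halted and a thorough investigation will take place before the re-opening of accrual may be considered". The stated purpose is to protect subjects from excessive toxicity. The SAP contains no stopping rule.

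Each subject may receive up to four implants, at least three months apart. The three decision paragraphs in section 5.1 base clearance on the subject's own imaging, markers, laboratory, examination and quality-of-life findings. For implant 2: "Assuming the subject is cleared, the second implantation will proceed as soon as possible". The paragraphs for implants 3 and 4 say the same ("Assuming the subject is cleared, the third implantation will proceed as soon as possible"; "Assuming the subject is cleared, the fourth implantation will proceed as soon as possible"). None of them refers to study-level deaths.

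Section 6.5.1 states that "the dose limiting toxicity (DLT) is most likely to be related to the number of implantations rather than the number of macrobeads implanted" at each procedure.

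Other safeguards exist:

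- Section 6.6: "The Safety Committee, as well as the investigators, will review each instance of Grade 5 adverse event".
- Section 6.1: "The Safety Data Monitoring Board will independently review all safety parameters and safety results in the study".
- Section 6.8: a dose-limiting toxicity (DLT), or toxicity of grade 2 or above, opens a discussion about removing the beads from that subject.
- Section 6.5: the study may be halted, among other grounds for unacceptable risk to enrolled patients, but "this action may be taken after appropriate consultation between the sponsor and investigator".

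**The concern.** Halting accrual stops first implants only. The exposure that section 6.5.1 singles out is the repeat implant, and the rule's operative text does not mention it. Read literally, implants 2–4 can continue while three possibly related deaths are being investigated. Once enrolment has closed, the halt has nothing left to act on, although the last subject may still have about nine months of implants to come.

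An implant given in that interval can be only partly undone. Section 6.7 puts likely bead removal at 50–70% and section 6.8 at 50–80%, so 20–50% of the beads would stay. The cells in them do die over 4 to 6 months (section 6.7). The human repeat-dose experience cited from Phase I is four second implants (section 5.1.25). More may have accumulated in this trial by Amendment 11, since section 7.1 says its colorectal data had already been used for planning, but the protocol does not report it.

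**Working it through.** **1. The plan's own figures.** Appendix 3 item 8 tabulates P(X ≥ 3) for X ~ Binomial(30, p).

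| True rate p | 5% | 10% | 20% | 30% |
|---|---|---|---|---|
| Stated, n = 30 | 19% | 59% | 96% | 99.8% |
| Recomputed, n = 30 | 18.8% | 58.9% | 95.6% | 99.8% |
| Same rule, n = 74 | 72.2% | 98.3% | >99.9% | >99.9% |

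The table reproduces, and neither it nor the trigger is disputed here. The n = 74 row uses the current planned number of implanted subjects and shows how often a hold would be invoked.

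**2. Which safeguard holds repeat implants when the trigger is met?**

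| Provision | Mandatory? | Holds implants 2–4 in all enrolled subjects? |
|---|---|---|
| 6.6 and Appendix 3 item 8, accrual halt and investigation | Yes | Not stated; both the halt and its lifting concern accrual |
| 6.6, review of each grade 5 event | Yes | No hold attached |
| 6.1, independent board review | Yes | No hold attached |
| 5.1, clearance before each implant | Yes | Subject's own findings only |
| 6.8, discussion of bead removal | Yes | That subject only |
| 6.5, study halt | No, discretionary | Possible, but not linked to the trigger |

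**3. Repeat implants falling due during an investigation.** The documents give no investigation length, attrition or event timing, so these are assumptions. With accrual r per month, 3-month spacing and at least nine months of prior accrual (steady state), the monthly number is:

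- no attrition: 3r
- exponential survival: r × Σ 0.5^(3k/median), k = 1, 2, 3
- half proceeding at each step: r × (0.5 + 0.25 + 0.125)

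| r per month | No attrition | 12-month median | 6-month median | Half proceed |
|---|---|---|---|---|
| 3 (Appendix 3 item 3) | 9.0 | 6.4 | 4.7 | 2.6 |
| 1 | 3.0 | 2.1 | 1.6 | 0.9 |
| 6.17 (= 74/12) | 18.5 | 13.2 | 9.6 | 5.4 |

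The range of r is needed because 3 per month for about 12 months gives 3 × 12 = 36 subjects, not 74; 74 would take 74/3 = 24.7 months. At r = 3, a one-month review spans about 3 to 9 implants and a three-month review about 8 to 27. The no-attrition ceiling over nine months is 9 × (3 + 2 + 1) = 54.

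An early trigger gives fewer. At a 20% true rate with deaths in months 0–4, the third event comes at a median of 6.2 months, and the no-attrition mean for the next month is 5.6, not 9. At 30% it is 4.1.

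**4. Chance that the third event falls after accrual closes.** This was simulated with 74 subjects entering evenly and each having a qualifying death with probability p. The probability is that the trigger is met and is met after the last first implant. At r = 3:

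| Assumed timing of death | p = 5% | p = 10% |
|---|---|---|
| Months 0–4 after first implant | 6% | 1% |
| Within 3 months of an implant, survival-weighted (6- or 12-month median) | 15–17% | 4–5% |
| Months 0–13 | 21% | 7% |
| Months 6–13 | 33% | 14% |

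At 20% and 30% it is near zero at this accrual rate. At p = 5% the range is 2–10% for r = 1 and 13–68% for r = 6.17.

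**The case against.** The strongest reply is that the protocol presents the rule as stopping the study. Its heading in section 6.6 concerns premature termination, and the row label in the Appendix 3 table speaks of stopping the study. That makes the intended scope partly ambiguous. It does not settle it, because the operative sentence names accrual both for the halt and for its lifting.

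Second, enrolled patients are not unprotected. A reader might infer that dosing must continue, or would continue without oversight, after three such deaths. The documents do not support that. Review starts with the first grade 5 event, each repeat implant needs clearance, and section 6.5 lets the DSMB, FDA, sponsor, investigator or monitor prompt a halt, expressly for risk to enrolled patients. What stands is narrower: no provision requires the hold when the trigger is met.

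Third, a reader might take section 6.5.1 as predicting deaths from repeat implants. It concerns DLT, mostly grade 3 or higher, and says nothing specific about deaths.

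Fourth, the magnitude should carry little weight. Nine implants per month is a steady-state ceiling without attrition, and the post-accrual gap all but disappears at high true rates with 3 subjects per month. Both limits are accepted.

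Fifth, a default hold has a price. Section 6.3 lets a death count as possibly related when underlying disease is a presumable cause, eligibility asks for a life expectancy of only 6 weeks, and beads function for about 3 to 4 months (section 4.2). Some patients could lose an implant to a hold that proves unnecessary.

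**Conclusion.** The point holds as a cheap improvement. On the text, the trigger halts accrual and starts an investigation. A hold on implants 2–4 is left to a discretionary decision under section 6.5. This rests on wording and needs no simulation.

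The size is illustrative: about 3 to 9 repeat implants per month of investigation at 3 subjects per month in steady state. The chance that the rule is first met when there is no accrual left to halt is about 6–33% at a 5% true rate and 1–14% at 10%. These figures depend on assumed accrual, attrition and timing of deaths. They show that the gap can matter, not that harm is expected.

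**What to change.** Amend section 6.6 and Appendix 3 item 8 in the same words, for example: *When the trigger is met, accrual stops and every further implantation, including implants 2–4 in enrolled subjects, is suspended until the DSMB has completed an expedited review of the deaths and agrees to resumption. The DSMB may release individual implants before its review ends. The rule applies for as long as any implantation remains to be given.*

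This takes two or three sentences in an amendment and uses the existing board. It needs no extra patients, procedures or analyses, and the trigger probabilities do not change. If the sponsor already intends such a hold, the text makes it explicit.

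The real cost is a possible short delay to repeat implants in patients with short life expectancy. It would not be rare: at a 5% true rate the trigger is met in 72% of 74-subject trials. Expedited review and individual release are there to limit that cost. Individual release does bring back case-by-case judgement, but with suspension as the default and the DSMB making the decision.
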